11.2. Sample Size/Accrual Rate

We plan 12-15 months of accrual for 45 patients (approximately 3-4 patients per month) and a minimum of 6 months follow-up.

Evaluable patients include study subjects who received at least one cycle of HD IL-2 and had later formal imaging and clinical assessment of tumor response to treatment and those who failed to return for imaging because of cancer specific death or clinical determination of progression. Non-evaluable subjects will be replaced.

With 45 evaluable subjects, we will have >90% power to declare a significant difference between an response rate of 20% or higher and 7% (the expected response rate of this population under standard care) by a 1-sided exact binomial test ($\alpha=0.1$).

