11. STATISTICAL CONSIDERATIONS

11.1. Study Design/Endpoints

This is a phase II study of high dose bolus interleukin-2 (HD IL2) in patients with advanced inoperable stage III or stage IV melanoma who have prior anti-PD1 immunotherapy. The safety of HD IL2 is well studied and will be monitored. The focus of the study is to evaluate the efficacy of this HD IL-2 in this specific patient population.

The primary endpoint is (CR+PR) as assessed by RECIST criteria version 1.1. The total accrual goal is 45 patients. We will follow a Bayesian design to establish sequential stopping rules for futility (Thall, Simon and Estey 1995). The expected response rate for this patient population is between 5 and 10%. We would consider the HD IL-2 worth further investigation if a response rate of 20% is achieved. Thus, if there is sufficient evidence that the response rate of the regiment is 7% or less, we will stop the accrual. Let p_0 and p_1 denote the response rate of the standard treatment and the HD IL-2 respectively, by sufficient evidence, we mean that the posterior probability, $\Pr(p_0 + 0.05 > p_1)$, exceeds 85%. Based on the existing data, it is safe to say that the response rate of the studied population under standard care is between 5 and 10%, therefore, we use a Beta(70,930) prior for the standard treatment, which corresponds to a distribution of the response rate centered at 7%. We set a flat prior, Beta(0.4,1.6), for the response rate of HD IL-2.

We will allow the accrual to continue without interruption for the first 10 patients. The stopping boundaries for futility after the “burning period” can be presented as tables of possible outcomes for efficacy as shown in the following table:

Table 1 Bayesian Stopping Rules

Stop the Accrual to if

Responses<=	in No. Pts
1	10-19
2	20-31
3	32-44
4	45

The operating characteristics of this design can expressed in terms of the probability of

stopping the study early when the regimen is effective (i.e. response rate>0.2) and ineffective (i.e. response rate<0.07) and the median sample size under each situation. The following table summarizes this probability and the median sample size under this design based on 10,000 simulations of hypothetical trials under different assumptions of true response rates.

Table 2 Frequentist Properties of the Stopping Rules

True Response Rate	Pr (Stop Early)	Median Sample Size
0.05	0.92	17.7
0.1	0.35	27.9
0.15	0.32	35.6
0.2	0.16	40.2
0.25	0.07	42.6
0.3	0.03	43.9

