11.3.1. Analysis Sets

Safety population-the data from all patients who received initial treatment of HD IL-2 will be used in the analyses of regimen safety.

Efficacy population- data from patients received at least one cycle of HD IL-2 will be used in the analysis of PFS and OS. For response rate, patients failed to return for

imaging due to reasons **other than** cancer-specific death or clinical determination of progression will not be included.

11.3.2. **Baseline Characteristics**

Baseline descriptive statistics will be provided for all evaluable patients. Statistical summaries will be reported for demographic variables (age, sex, race/ethnicity), performance status, laboratory parameters, and disease characteristics.

11.3.3. **Analysis of Clinical Response**

All patients included in the study will be assessed for response to treatment, even if there are major protocol treatment deviations or if they are ineligible. Each patient will be assigned one of the following categories: 1) complete response, 2) partial response, 3) stable disease, 4) progressive disease, 5) early death from malignant disease, 6) early death from toxicity, 7) early death because of other cause, or 9) unknown (not assessable, insufficient data).

All of the patients who met the eligibility criteria and completed at least one cycle of IL2 should be included in the main analysis of the response rate. Response rate will be estimated by the proportion of patients with a best response of complete response (CR), partial response (PR) by RECIST criteria, with corresponding exact 90% confidence limits being reported. The distribution of response duration (time to progression among patients achieving CR or PR) will be characterized by median and quartiles, with the corresponding Kaplan-Meier estimate being made of PFS among patients responding to treatment.

11.3.4. **Survival**

PFS will be measured from the initial date of treatment to the date of documented progression, or the date of death (in the absence of progression).

OS will be measured from the initial date of treatment to the recorded date of death.

PFS and OS will be estimated by the Kaplan-Meier method. The corresponding median survival times (with 90% confidence limits) will be determined, as will the cumulative percentage of patients remaining progression-free (and the cumulative percentage- alive) at selected time points after initial treatment (e.g., 3, 6, 12, 18 months).

11.3.5. **Safety**

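### The stated power above 90% is for a fixed sample of 45 and leaves out the futility stopping rule; with that rule, power at a 20% response rate is about 81%

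*Combined protocol and SAP*

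**What the plan says.** Section 11.2 gives the only power statement in the plan: "With 45 evaluable subjects, we will have >90% power to declare a significant difference between an response rate of 20% or higher and 7" per cent, using a one-sided exact binomial test at alpha 0.1. It does not mention interim stopping.

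Section 11.1 describes a sequential design: "We will follow a Bayesian design to establish sequential stopping rules for futility". The text says "if there is sufficient evidence that the response rate of the regiment is 7% or less, we will stop the accrual", and defines sufficient evidence as a posterior probability Pr(p0 + 0.05 > p1) above 85%. The priors are Beta(70,930) for standard care and Beta(0.4,1.6) for HD IL-2. Monitoring starts after a run-in: "We will allow the accrual to continue without interruption for the first 10 patients". Table 1 prints stopping limits. Table 2, headed "Table 2 Frequentist Properties of the Stopping Rules", gives a 0.16 probability of stopping early at a true rate of 20%.

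Section 11.3.3 describes the response analysis as an estimated proportion "with corresponding exact 90% confidence limits being reported". No section states how many responses would count as success, and none calls the futility rule non-binding.

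**The concern.** The power sentence describes a different design from the one in section 11.1. Under a futility rule, some trials of a truly active regimen stop early and can no longer reach a positive result, so power must be lower than for a fixed sample of 45. Section 11.1 names 20% as the rate that would make HD IL-2 worth further study. A reader relying on section 11.2 would put the chance of missing such a regimen below 10%. Table 2 shows the early-stopping part of the loss, but no passage combines it with the final test.

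**Working it through.** **Inputs.** n = 45, null rate 7%, target rate 20%, one-sided exact test at alpha 0.1 (section 11.2). Beta(70,930) and Beta(0.4,1.6) priors, 85% posterior criterion with the 0.05 shift, first look at patient 10 (section 11.1). The success cutoff is not stated and is inferred from the exact test.

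**1. Reproduce the stated power (no stopping), X ~ Binomial(45, p).**

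| Cutoff | P(X ≥ r given 7%) | P(X ≥ r given 20%) |
|---|---|---|
| ≥5 | 0.205 | 0.962 |
| ≥6 | 0.092 | 0.910 |
| ≥7 | 0.036 | 0.823 |

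The smallest cutoff with alpha at or below 0.10 is 6, with power 0.910. The stated figure reproduces, but only as a single-stage test.

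**2. Upper limit from Table 2 alone.** Power at 20% ≤ 1 − Pr(stop early) = 1 − 0.16 = 0.84. This needs no assumption about Table 1 or the final cutoff.

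**3. Boundary implied by the criterion.** With x responses in n patients, p1 ~ Beta(0.4 + x, 1.6 + n − x) and p0 ~ Beta(70,930). Stop if Pr(p0 + 0.05 > p1) > 0.85. Numerical integration at the change points gives:

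- 1/18: 0.833, continue; 1/19: 0.851, stop
- 2/30: 0.842, continue; 2/31: 0.856, stop
- 3/41: 0.844, continue; 3/42: 0.855, stop

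So the rule stops at 0 responses in 10–18 patients, ≤1 in 19–30, ≤2 in 31–41 and ≤3 in 42–45.

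**4. Check that boundary against Table 2.** Exact patient-by-patient recursion, looking after every patient from 10:

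| True rate | Pr(stop), computed | Pr(stop), Table 2 | Mean N, computed | Sample size, Table 2 |
|---|---|---|---|---|
| 0.05 | 0.916 | 0.92 | 17.7 | 17.7 |
| 0.10 | 0.604 | 0.35 | 27.9 | 27.9 |
| 0.15 | 0.320 | 0.32 | 35.6 | 35.6 |
| 0.20 | 0.155 | 0.16 | 40.2 | 40.2 |
| 0.25 | 0.073 | 0.07 | 42.6 | 42.6 |
| 0.30 | 0.034 | 0.03 | 43.9 | 43.9 |

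Eleven of the twelve cells agree, so this is evidently the boundary behind the plan's own simulations. (The 0.35 is a separate point. The column labelled as a median matches the mean.)

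**5. Power of the combined rule.** Success = not stopped and at least 6 responses in 45.

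- At 20%: 0.155 stop early and 0.038 reach 45 with fewer than 6 responses, so power = 1 − 0.155 − 0.038 = 0.807.
- At 7%: type I error = 0.069, down from 0.092.
- Power reaches 90% only at a true rate of about 23.8%.

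Stopping on this boundary forfeits no trial that was already significant: 3/42, for example, has a one-sided p-value of 0.57 against 7%.

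**6. Sensitivity at 20%.**

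| Variation | Power |
|---|---|
| Looks only at 10, 20, 30, 40 and 45 | 0.815 |
| No looks after patient 36 | 0.807 |
| Cutoff ≥5/45 (type I error 0.133, above 0.10) | 0.836 |
| Cutoff ≥7/45 | 0.746 |
| Criterion without the 0.05 shift | 0.850 |
| Table 1 as printed, cutoff ≥6/45 (type I error 0.035) | 0.573 |

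The ≥7/45 row is what success would require if it meant that the exact 90% interval lies above 7%: the lower limit is 7.5% at 7/45 and 6.0% at 6/45. Table 1 as printed stops at 1/10 and 4/45, where the posterior probabilities are only 0.605 and 0.756.

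**The case against.** The sentence in section 11.2 is conditional on 45 evaluable subjects and names a single test. On those terms it is correctly calculated, and Table 2 discloses the stopping probability just before it. This is fair: the fault is leaving out the stopping rule, not a slip in the binomial arithmetic. But the sentence is the only power claim for the study, and 0.910 is not the power conditional on reaching 45 patients either. That would be 0.807/0.845, about 95.5%.

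The second objection is stronger. The 81% rests on a boundary the plan does not print and on a cutoff it does not state, and Table 1 taken literally gives 57%. That stands as a limit on the exact value, though not on the conclusion. The cap of 84% needs neither assumption, and no variation in the sensitivity table reaches 90%. Reading the rule literally as stopping for evidence of 7% or less, without the 0.05 shift, still gives only 0.850.

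Finally, the calculation treats responses as known at once and stopping as binding. Response is assessed at week 8, so patients enrolled before a stop takes effect could move power upward, somewhere between about 81% and 91%. The plan does not describe such an allowance, and removing the late looks leaves the result at 0.807.

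**Conclusion.** The concern holds. Power above 90% belongs to a fixed-sample test, not to the design in section 11.1. With the futility boundary implied by the stated priors and criterion, power at 20% is about 81%, roughly 10 points lower, and the miss rate rises from 9.0% to 19.3%. The figure assumes binding stopping after each patient from the tenth, immediate response information and success at 6 or more of 45. The direction, and the 84% ceiling given Table 2, do not depend on the inferred boundary or cutoff. The misstatement concerns power only: type I error falls, so there is no added false-positive risk. It should be fixed.

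**What to change.** First, reconcile Table 1 with the posterior criterion. Its printed limits are about one response stricter than the criterion implies, and the power statement cannot be settled until one boundary is declared operative.

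Then replace the power sentence with a success criterion and the operating characteristics of the combined rule. If the boundary derived from the criterion is adopted, suitable wording is: *Success is defined as not stopped for futility and at least 6 responses in 45 evaluable patients. With futility monitoring after each patient from patient 10, treated as binding and with responses assumed known at each look, the design has about 81% power at a true response rate of 20% and a one-sided type I error of about 7% at a rate of 7%.*

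If Table 1 is kept as printed, the sentence must instead give about 57% power and 3.5% type I error.

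The power sentence and success definition are wording changes, but the choice between Table 1 and the criterion settles an operative stopping boundary. No extra patients are needed. The cost is a less favourable stated power.

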11.3. Statistical Analyses

The study will be analyzed 6 months after the accrual is finished.

11.3.1. Analysis Sets

Safety population-the data from all patients who received initial treatment of HD IL-2 will be used in the analyses of regimen safety.

Efficacy population- data from patients received at least one cycle of HD IL-2 will be used in the analysis of PFS and OS. For response rate, patients failed to return for

imaging due to reasons **other than** cancer-specific death or clinical determination of progression will not be included.

11.3.2. **Baseline Characteristics**

Baseline descriptive statistics will be provided for all evaluable patients. Statistical summaries will be reported for demographic variables (age, sex, race/ethnicity), performance status, laboratory parameters, and disease characteristics.

11.3.3. **Analysis of Clinical Response**

All patients included in the study will be assessed for response to treatment, even if there are major protocol treatment deviations or if they are ineligible. Each patient will be assigned one of the following categories: 1) complete response, 2) partial response, 3) stable disease, 4) progressive disease, 5) early death from malignant disease, 6) early death from toxicity, 7) early death because of other cause, or 9) unknown (not assessable, insufficient data).

All of the patients who met the eligibility criteria and completed at least one cycle of IL2 should be included in the main analysis of the response rate. Response rate will be estimated by the proportion of patients with a best response of complete response (CR), partial response (PR) by RECIST criteria, with corresponding exact 90% confidence limits being reported. The distribution of response duration (time to progression among patients achieving CR or PR) will be characterized by median and quartiles, with the corresponding Kaplan-Meier estimate being made of PFS among patients responding to treatment.

11.3.4. **Survival**

PFS will be measured from the initial date of treatment to the date of documented progression, or the date of death (in the absence of progression).

OS will be measured from the initial date of treatment to the recorded date of death.

PFS and OS will be estimated by the Kaplan-Meier method. The corresponding median survival times (with 90% confidence limits) will be determined, as will the cumulative percentage of patients remaining progression-free (and the cumulative percentage- alive) at selected time points after initial treatment (e.g., 3, 6, 12, 18 months).

11.3.5. **Safety**

Toxicity will be primarily evaluated by examining the number of doses of HD IL-2 administered during a cycle of therapy. Based on previous experience with high dose IL2 at the University of Pittsburgh, the median number of doses per course 1 (first 2 cycles) as monotherapy [16], is 16 (range 8-26) and in sequential combination with temozolomide [21], is 15 (range 7-23). As a result, the median number of doses per course 1 will be considered in addition to toxicity reported via CTCAE criteria.

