10.1.1. Definitions

Evaluable for toxicity. All patients will be evaluable for toxicity from the time of their first protocol drug administration.

Evaluable for objective response. Only those patients who have measurable disease present at baseline, have received at least course 1 of therapy, and have had their disease re-evaluated will be considered evaluable for response. These patients will have their response classified according to the definitions stated below. (Note: Patients who exhibit objective disease progression prior to the end of course 1 will also be considered evaluable.)

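### The denominator of the primary response rate is defined inconsistently across Sections 10.1.1, 11.2, 11.3.1 and 11.3.3, and no rule says which governs

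*Combined protocol and SAP*

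**What the plan says.** Four sections define who counts for response.

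- **10.1.1 Definitions.** Patients must have measurable disease at baseline, and must "have received at least course 1 of therapy, and have had their disease re-evaluated will be considered evaluable for response". A course is two cycles (5.1). The one exception is: "Patients who exhibit objective disease progression prior to the end of course 1 will also be considered evaluable".
- **11.2 Sample Size/Accrual Rate.** Evaluable patients received at least one cycle and were later imaged and assessed. Without imaging, only "those who failed to return for imaging because of cancer specific death or clinical determination of progression" also count. Then: "Non-evaluable subjects will be replaced". The power statement uses this set: "With 45 evaluable subjects, we will have >90% power".
- **11.3.1 Analysis Sets.** For the response rate, patients not imaged for any reason other than "cancer-specific death or clinical determination of progression will not be included".
- **11.3.3 Analysis of Clinical Response.** For the response rate, the rule here is: "All of the patients who met the eligibility criteria and completed at least one cycle of IL2 should be included in the main analysis". No imaging condition is attached. The response categories in the same section include "6) early death from toxicity, 7) early death because of other cause" and a category for unknown.

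Table 1 in 11.1 gives the futility boundaries by number of patients, without saying which of these sets is counted.

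**The concern.** Response rate is the primary endpoint, and its denominator feeds three things: the final exact test, the reported estimate with its 90% limits, and the Table 1 counts that decide whether accrual stops. If the denominator is open, it can be settled after responses are known.

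The direction also matters. A patient who dies of toxicity, or stops for toxicity and is never imaged, cannot be a documented CR or PR. Dropping and replacing such patients raises the estimated response rate. The course requirement in 10.1.1 can work the other way, because it can remove a responder who was imaged after a single cycle, although 5.1 continues response assessment when full treatment is not given.

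**Working it through.** **Step 1. The sections side by side.**

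| Patient | 10.1.1 | 11.2 | 11.3.1 | 11.3.3 |
|---|---|---|---|---|
| A. Eligible, completed one cycle, no imaging because of toxicity | out | out, replaced | out | in, non-responder |
| B. Eligible, completed one cycle, imaged, no progression | out | in | in | in |
| C. Eligible, completed one cycle, not imaged because of clinical progression or cancer death | out | in | in | in |
| D. Ineligible, completed two cycles, imaged | in | in | in | out |

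No two of 10.1.1, 11.2/11.3.1 and 11.3.3 give the same set.

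**Step 2. Reproduce the plan's power.** Inputs from 11.2: n = 45, 7% against 20%, one-sided exact binomial, alpha 0.10. With X the number of responders:

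- P(X ≥ 5 | 45, 0.07) = 0.205, too high.
- P(X ≥ 6 | 45, 0.07) = 0.0923, so the cutoff is 6.
- P(X ≥ 6 | 45, 0.20) = 0.9098, which agrees with the stated figure of more than 90%.

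The power figure is sound for 45 evaluable patients. The problem is the denominator.

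**Step 3. One patient at the cutoff.**

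| Result | Rate | Exact 90% limits | p against 7% |
|---|---|---|---|
| 6/45 | 13.3% | 6.0–24.6% | 0.0923 |
| 6/46 (patient A added) | 13.0% | 5.8–24.1% | 0.1002 |
| 5/44 (a responder of type B removed) | 11.4% | not needed | 0.192 |

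The first result meets 0.10 and the other two do not. With Table 1 applied as printed after every patient from 10 to 44, the chance of ending at exactly 6/45 is 1.8%, 5.1% or 2.7% at true rates of 7, 15 or 20%. The intervals for 6/45 and 6/46 both include 7%.

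**Step 4. Interim counts.** Table 1 continues at 2 responses in 19 and stops at 2 in 20. It continues at 3 in 31 and stops at 3 in 32. One un-imaged patient can decide whether accrual stops. There is no row above 45, although replacement can take enrolment beyond 45.

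**Step 5. Mixed use.** Suppose accrual runs to 45 evaluable patients (11.2) and 46 to 50 are then analysed (11.3.3). The smallest cutoff with exact alpha at most 0.10 moves from 6 to 7 (alpha 0.040 to 0.058). Power at 20% is then 0.841, 0.856, 0.871, 0.884 and 0.897 for n = 46 to 50, against 0.910.

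**Step 6. Bias from dropping non-responders.** Let d be the share of the 11.3.3 set that is dropped, all non-responders. The documents do not give d; 5% and 10% are assumptions. The evaluable-set rate is p/(1 − d).

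- 0.07/0.95 = 7.4% and 0.07/0.90 = 7.8%.
- 0.20/0.95 = 21.1% and 0.20/0.90 = 22.2%.

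If 7% is the rate in the 11.3.3 set, P(X ≥ 6 | 45) at the inflated rate is the type I error:

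| d | Fixed test in 11.2 | Table 1 as printed, then ≥ 6/45 |
|---|---|---|
| 0 | 0.092 | 0.035 |
| 5% | 0.111 | 0.042 |
| 10% | 0.134 | 0.052 |

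If 7% refers to evaluable patients, the test keeps its level.

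**The case against.** **11.2 and 11.3.1 agree, and 11.3.1 could limit 11.3.3.** The section on analysis sets speaks directly about response rate, and the 11.3.3 categories apply to everyone in the study, not only the main analysis. This reading is possible. But nothing states it, and 11.3.3 names its own set as the main analysis. It would also leave 10.1.1 in conflict with 11.2 on course against cycle, and on objective progression against clinical progression or cancer death.

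**10.1.1 may not require two cycles.** Because 5.1 allows for incomplete treatment with assessment at the end of the course, a one-cycle patient imaged at that time might be read as evaluable. That would remove the 5/44 example. It would not bring patient A back in, since re-evaluation is still required.

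**The effect is small and conditional.** This stands. The Study Calendar schedules imaging at week 8 and off study, so a patient who stops for toxicity should usually be imaged. The 6/45 case is uncommon, and the shares in Step 6 are assumed. With Table 1 applied, type I error stays below 0.10.

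**The Table 1 figures combine a sequential rule with a final test of at least 6/45.** No section specifies that combination, as Table 1 by itself passes 5/45. The figures should be read as illustrating that combination only. The contradiction does not depend on them.

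**Aligning 11.3.3 to 11.2 would also end the conflict and keep power at 0.910.** It would, but at the price of removing toxicity failures from the primary estimate.

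**Conclusion.** The concern holds, and one denominator must be fixed before analysis. The contradiction is in the current text and needs no assumption. Its numerical effect does: it depends on how many patients of types A to D occur, which the documents do not say and which may be few. At the boundary a single patient reverses the test. Away from it, an assumed 5 or 10% of dropped non-responders adds 0.4 or 0.8 percentage points to a 7% rate, and 1.1 or 2.2 points to a 20% rate. The correction is required because the primary result and the futility counts are not uniquely defined, not because a large bias has been shown.

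**What to change.** - Use the 11.3.3 set (eligible, completed at least one cycle) as the single primary response denominator, and carry it into 10.1.1, 11.2 and 11.3.1.
- Use one exposure term throughout and define it. At present 11.2 and 11.3.1 speak of receiving a cycle and 11.3.3 of completing one, while a cycle has a maximum number of doses but no minimum.
- Count patients in the set without a documented CR or PR as non-responders, and do not remove or replace them in the primary analysis.
- State that Table 1 counts this set.
- Keep the imaging-evaluable set of 11.2 as a sensitivity analysis.
- State which set the 7%, 20% and power figures refer to, and restate the power if they refer to evaluable patients only.

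An all-treated set would be an acceptable alternative, not a required correction. The PFS and OS set needs no change.

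**Cost.** The reported response rate may be slightly lower. If 20% refers to the 11.3.3 set, the change costs no power. If 20% was meant for imaging-evaluable patients, the rate in the new set is 0.20 × (1 − d), that is 19% or 18% for the assumed d of 5 or 10%. Power with 45 patients then falls from 0.910 to 0.881 or 0.844 for the fixed test, and from 0.573 to 0.533 or 0.491 with Table 1 as printed followed by at least 6/45. No new sample size is proposed here, because it depends on how Table 1 is applied.

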10.1.2. Duration of Response

Duration of overall response: The duration of overall response is measured from the time measurement criteria are met for CR or PR (whichever is first recorded) until the first date that recurrent or progressive disease is objectively documented (taking as reference for progressive disease the smallest measurements recorded since the treatment started).

The duration of overall CR is measured from the time measurement criteria are first met for CR until the first date that recurrent disease is objectively documented.

Duration of stable disease: Stable disease is measured from the start of the treatment until the criteria for progression are met, taking as reference the smallest measurements recorded since the treatment started.

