10.1.3. Progression-Free Survival

PFS is defined as the duration of time from start of treatment to time of progression (or death if there is no progression date). Patients with neither a progression date nor date of death will be censored as of last contact.

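### The only estimator that 11.3.3 names for response duration is PFS among responders, which starts at first treatment and counts death; 10.1.2 starts at first CR/PR and names only recurrence or progression

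*Combined protocol and SAP*

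**What the plan says.** Section 10.1.2 fixes the start of response duration: "The duration of overall response is measured from the time measurement criteria are met for CR or PR", taking whichever of the two is recorded first. It runs "until the first date that recurrent or progressive disease is objectively documented". Death is not named as an end event, and the section gives no censoring rule.

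Section 10.1.3 says "PFS is defined as the duration of time from start of treatment to time of progression", with death as the event when there is no progression date and censoring at last contact. Section 11.3.4 repeats the starting point: "PFS will be measured from the initial date of treatment to the date of documented progression", or to death in the absence of progression.

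Section 11.3.3 then describes the analysis: "The distribution of response duration (time to progression among patients achieving CR or PR) will be characterized by median and quartiles". The same sentence of the plan goes on to name the estimation method: "with the corresponding Kaplan-Meier estimate being made of PFS among patients responding to treatment". It gives no starting point for response duration and does not refer to 10.1.2. Nothing in the document gives PFS among responders a different start.

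**The concern.** Response duration and PFS among responders are different quantities. They differ in starting point (first CR/PR against first treatment) and in end event (progression or recurrence against progression or death).

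The starting point matters because patients are selected on response. A patient can enter the responder group only by remaining progression-free until a scan shows CR or PR. If the clock starts at first treatment, that stretch is event-free by construction and is reported as though it were time in response.

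At stake is how durable the responses appear. Section 2.1 gives prolonged durable responses in some patients as the basis for approval of HD IL-2, and 2.2 quotes a historical median response duration. Readers of a single-arm trial are likely to look at this figure even though it carries no formal test.

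**Working it through.** **The plan's own figures.** The document states no figure for response duration. The nearby design figure, power above 90% for 20% against 7% with 45 evaluable patients and a one-sided exact test at 0.1 (11.2), does reproduce. Requiring at least 6 responses of 45 gives exact alpha 0.0923 and power 0.9098 as a fixed-sample test. The present point does not depend on it.

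**Inputs**
- First response assessment: 8 weeks, plus or minus 1 week (section 9).
- At most 3 courses, each followed by an assessment (5.1): about weeks 8, 16 and 24 without delays.
- Analysis 6 months after accrual ends (11.3).
- Median response duration of 8.9 months (2.2), used here only as an assumed value for scale.

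**Identity.** For a responder who later progresses,

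PFS = time to first CR/PR + duration of response.

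If all responses are first recorded at the same time t, the median of the sum is the median duration plus t. This holds for any distribution of duration, ignoring censoring and deaths. Weeks convert to months as weeks × 12/52.1775.

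| First CR/PR recorded | t (months) | Median from first CR/PR | Median as PFS | Shift |
|---|---|---|---|---|
| week 7 | 1.61 | 8.9 | 10.5 | +18% |
| week 8 | 1.84 | 8.9 | 10.7 | +21% |
| week 9 | 2.07 | 8.9 | 11.0 | +23% |
| week 16 | 3.68 | 8.9 | 12.6 | +41% |
| week 24 | 5.52 | 8.9 | 14.4 | +62% |

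The relative shift depends on the assumed median. For week 8 it is 1.84/4 = 46%, 1.84/6 = 31% and 1.84/12 = 15%.

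**Event-free proportions.** Assume an exponential duration with median 8.9 months and all responses at week 8.
- At 3 months: from first response, 2^(−3/8.9) = 79%; as PFS, 2^(−(3 − 1.84)/8.9) = 91%.
- At 6 months: 2^(−6/8.9) = 63% against 2^(−(6 − 1.84)/8.9) = 72%.
- If every response were first recorded at week 16 or later, 3-month PFS among responders would be 100% by construction, since 3.68 > 3.

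**Censoring.** A patient who starts treatment as accrual closes and responds at week 8 has about 6 − 1.84 = 4.2 months of observed response at the analysis. Ongoing responses are therefore likely, and a median with quartiles then needs a method that handles censoring. The PFS curve is the only such method that 11.3.3 names.

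**Number of responders.** 45 × 0.07 = 3.15 and 45 × 0.20 = 9, so about 3 to 9 patients contribute.

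**The case against.** The best reply is that 11.3.3 describes two outputs: response duration as defined in 10.1.2, summarised by median and quartiles, and beside it a PFS curve in responders. On that reading there is ambiguity but no contradiction. The reading is possible. It is strained by the word that ties the Kaplan-Meier estimate to the response-duration summary as its counterpart. It would also leave response duration with no stated start in 11.3.3 and no method for responses still ongoing at the analysis. The passage needs repair either way.

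Four limits on the point do stand.
- **Net direction.** A reader might infer that the reported duration will be too long by the whole time to response. The documents do not support that. PFS counts deaths without progression and 10.1.2 does not, so such deaths could shorten the PFS-based figure and offset part of the lead-in.
- **Upper end.** The +62% needs every response to be first recorded at week 24, and nothing in the document suggests that timing. Section 5.1 also allows local variation in schedule, so even 7 to 9 weeks is only the on-schedule range.
- **Benchmark.** A reader might infer that the result could not be compared with the historical 8.9 months. Section 2.2 does not say where that clock started, and no comparison is planned. All that can be said is that comparability cannot be assumed.
- **Importance.** Response duration is not among the objectives in 1.1 and 1.2, and no test or decision rests on it. With so few responders its median will be imprecise from either starting point.

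**Conclusion.** As written, 11.3.3 is wrong on its most natural reading: the estimate it attaches to response duration has a different start and a different end event from the definition in 10.1.2. For a response at the first scheduled assessment, the added guaranteed progression-free time is about 1.6 to 2.1 months. It rises to about 3.7 or 5.5 months for a response first recorded after course 2 or 3.

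The percentages are illustrations. They rest on an assumed median, a common time of first response and no censoring, with an exponential shape for the event-free proportions. The net effect also depends on deaths without progression, which the document gives no basis to estimate.

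This is a minor error in a secondary descriptive analysis. It would be going too far to conclude that the trial's main result is compromised: response rate, sample size and futility rule do not use response duration.

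**What to change.** In 11.3.3, replace the clause "with the corresponding Kaplan-Meier estimate being made of PFS among patients responding to treatment" with a Kaplan-Meier estimate of duration of response, starting at first documented CR or PR as in 10.1.2 and citing that section. In the same place:

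- state whether a death without documented progression is an event or is censored, and bring 10.1.2 into line;
- state the censoring date for responses still ongoing at the analysis;
- report time to first response separately;
- label any PFS curve in responders as a separate summary that starts at first treatment.

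The cost is a few lines of wording. The response and progression assessments that supply the dates are already in the plan, so no new data are needed. The drawback is that the reported median will probably be shorter.
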